10.2 Additional safety monitoring

10.2.1 Liver safety monitoring

To ensure participant safety and enhance reliability in determining the hepatotoxic potential of an investigational drug, a standardized process for identification, monitoring and evaluation of liver events has to be followed.

Please refer to [Table 16-1](#) in [Appendix 3](#) for complete definitions of liver laboratory triggers.

Once a participant is exposed to study treatment, every liver event defined in [Table 16-2](#) should be followed up by the investigator or designated personnel at the trial site, as summarized below. Additional details on actions required in case of liver events are outlined in [Table 16-2](#). Repeat liver chemistry tests (i.e., ALT, AST, TBL, PT/INR, ALP and G-GT) to confirm elevation.

- These liver chemistry repeats should be performed using the local laboratory used by the site. Repeated laboratory test results must be reported as appropriate.
- If the initial elevation is confirmed, close observation of the participant will be initiated, including consideration of treatment interruption if deemed appropriate.
- Hospitalization of the participant if appropriate
- Causality assessment of the liver event

- Thorough follow-up of the liver event should include
 - Based on investigator's discretion: serology tests, imaging and pathology assessments, hepatologist's consultancy; obtaining more detailed history of symptoms and prior or concurrent diseases, history of concomitant drug use, exclusion of underlying liver disease

All follow-up information and procedures performed must be recorded as appropriate in the CRF.

10.2.2 Data Monitoring Committee

This study will include a Data Monitoring Committee (DMC) which will function independently of all other individuals associated with the conduct of this clinical trial, including the site investigators participating in the study. The committee will include Novartis employees and at least one external medical expert. The DMC will assess at defined intervals the progress of a clinical trial, safety data, and critical efficacy variables and recommend to the sponsor whether to continue, modify, or terminate a trial.

Specific details regarding composition, responsibilities, data monitoring, and meeting frequency, and documentation of DMC reports, minutes, and recommendations will be described in a separate charter that is established between the sponsor and the DMC

11 Data Collection and Database management

11.1 Data collection

All data should be recorded, handled, and stored in a way that allows its accurate reporting, interpretation, and verification.

Designated investigator staff will enter the data required by the protocol into the Electronic Case Report Forms (eCRF). The eCRFs have been built using fully validated secure web-enabled software that conforms to 21 CFR Part 11 requirements. Investigator site staff will not be given access to the electronic data capture (EDC) system until they have been trained. Automatic validation programs check for data discrepancies in the eCRFs, allow modification and/or verification of the entered data by the investigator staff.

The investigator/designee is responsible for assuring that the data (recorded on CRFs) (entered into eCRF) is complete, accurate, and that entry and updates are performed in a timely manner. The Investigator must certify that the data entered are complete and accurate.

After final database lock, the investigator will receive copies of the participant data for archiving at the investigational site.

All data should be recorded, handled, and stored in a way that allows its accurate reporting, interpretation, and verification.

11.2 Database management and quality control

Novartis personnel (or designated Clinical Research Organization (CRO)) will review the data entered by investigational staff for completeness and accuracy. Electronic data queries stating

the nature of the problem and requesting clarification will be created for discrepancies and missing values and sent to the investigational site via the EDC system. Designated investigator site staff are required to respond promptly to queries and to make any necessary changes to the data.

Concomitant treatments and prior medications entered into the database will be coded using the WHO Drug Reference List, which employs the Anatomical Therapeutic Chemical (ATC) classification system. Medical history/current medical conditions and adverse events will be coded using the Medical Dictionary for Regulatory Activities (MedDRA) terminology.

Screenings, randomizations, exit statuses, as well as randomization codes and data about all treatment arms assigned to the participant will be tracked using an Interactive Response Technology (IRT).

Once all the necessary actions have been completed and the database has been declared to be complete and accurate, it will be locked and made available for data analysis/moved to restricted area to be accessed by independent programmer and statistician. Any changes to the database after that time can only be made after written agreement by Novartis development management

11.3 Site monitoring

Before study initiation, at a site initiation visit or at an investigator's meeting, a Novartis representative will review the protocol and data capture requirements (i.e. eSource Direct Data Entry (DDE) or eCRFs) with the investigators and their staff. During the study, Novartis employs several methods of ensuring protocol and GCP compliance and the quality/integrity of the site's data. The field monitor will check the completeness of participant records, the accuracy of data capture / data entry, the adherence to the protocol and to GCP, the progress of enrollment, and to ensure that study treatment is being stored, dispensed, and accounted for according to specifications. Key study personnel must be available to assist the field monitor during these visits. Continuous remote monitoring of each site's data may be performed by a centralized Novartis clinical research associate organization. Additionally, a central analytics organization may analyze data & identify risks & trends for site operational parameters and provide reports to Novartis clinical teams to assist with trial oversight.

The investigator must maintain source documents for each participant in the study, consisting of case and visit notes (hospital or clinic medical records) containing demographic and medical information, laboratory data, electrocardiograms, and the results of any other tests or assessments. All information on CRFs must be traceable to these source documents in the participant's file. The investigator must also keep the original ICF signed by the participant (a signed copy is given to the participant).

The investigator must give the monitor access to all relevant source documents to confirm their consistency with the data capture and/or data entry. Source data verification may be done on-site, if possible, or remotely, if the field monitor does not have access or have limited access to the site due to the current COVID-19 pandemic. Different approaches can be used depending on site medical records, and some of them could include sharing the information through electronic systems or platforms provided by a third party. In all cases investigator and sponsor must adhere to the recommendations established by the applicable Health Authorities.

Novartis monitoring standards require full verification for the presence of informed consent, adherence to the inclusion/exclusion criteria, documentation of SAEs, and of data that will be used for all primary variables. Additional checks of the consistency of the source data with the CRFs are performed according to the study-specific monitoring plan. No information in source documents about the identity of the participants will be disclosed.

12 Data analysis and statistical methods

Any data analysis carried out independently by the investigator should be submitted to Novartis before publication or presentation. The analysis will be conducted on all participant data at the time the trial ends.

12.1 Analysis sets

For all analysis sets, participants will be analyzed according to the study treatment(s) randomized.

The Safety analysis set will include all randomized participants that have received any study drug.

Commercially Confidential Information

The PD analysis set will include all randomized participants with no protocol deviations with relevant impact on PD data.

12.2 Participant demographics and other baseline characteristics

Demographic and other baseline data including disease characteristics will be listed and summarized descriptively by treatment group. Categorical data will be presented as frequencies and percentages. For continuous data, mean, standard deviation, median, minimum, and maximum will be presented.

Relevant medical histories and current medical conditions at baseline will be listed and summarized by system organ class and preferred term by treatment group.

12.3 Treatments

The Safety set will be used for the analyses below. Categorical data will be summarized as frequencies and percentages. For continuous data, mean, standard deviation, median, 25th and 75th percentiles, minimum, and maximum will be presented.

The dates and times of MAS825 dosing will be listed.

Concomitant medications and significant non-drug therapies prior to and after the start of the study treatment will be listed and summarized according to the Anatomical Therapeutic Chemical (ATC) classification system, by treatment group.

12.4 Analysis of the primary endpoint(s)/estimand(s)

The primary aim of the study is to evaluate the effect of MAS825 compared with placebo on the APACHE II score. A decrease in the score is considered a favourable outcome.

12.4.1 Definition of primary endpoint(s)/estimand(s)

The primary estimand, including the primary endpoint is defined in [Section 2.1](#) of this protocol. It is based on the APACHE-II score.

12.4.2 Statistical model, hypothesis, and method of analysis

The primary endpoint will be evaluated by an analysis of covariance model including treatment group and the three stratification factors as factors and baseline APACHE-II score as a covariate. The analysis will be performed on the safety analysis set. The mean differences of MAS825 vs placebo will be reported with 90% confidence intervals (CIs). The 1-sided p-value for the overall treatment factor will be reported.

The primary objective will be achieved if the null hypothesis that MAS825 is not different to placebo is rejected using a one side alpha of 10%.

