Study population	
Approximately 120 male and female patients aged 18 years and above .
 
The study population includes adult male and female SARS-CoV-2 infected patients who are hospitalized and diagnosed with COVID-19 pneumonia and impaired respiratory function.

Key Inclusion criteria	
Participants eligible for inclusion in this study must meet all of the following criteria:
 
1. Male and female patients aged ≥ 18 years at screening2. Signed Informed Consent Form (ICF) by patient capable of giving consent, or, when the patient is not capable of giving consent, by his or her legal/authorized representative (if allowed according to local requirements)3. Clinically diagnosed with the SARS-CoV-2 virus by polymerase chain reaction (PCR) or by other approved diagnostic methodology within 7 days prior to randomization4. Hospitalized with COVID-19-induced pneumonia evidenced by chest x-ray, computed tomography scan (CT scan) or magnetic resonance scan (MR scan) (taken within 5 days prior to randomization)5. Impaired respiratory function, defined as peripheral oxygen saturation (SpO_2) $\leq 93\%$ on room air or partial pressure of oxygen (PaO_2) / fraction of inspired oxygen (FiO_2) < 300 millimeter of mercury (mmHg) at time of screening For cities located at altitudes greater than 2500 m above sea level, these will be substituted with $\text{SpO}_2 < 90\%$ and $\text{PaO}_2/\text{FiO}_2 < 250$ mmHg6. Acute Physiologic Assessment and Chronic Health Evaluation (APACHE) II score of ≥ 10 at time of screening7. CRP ≥ 20 mg/L or ferritin level ≥ 600 $\mu\text{g}/\text{L}$ at screening8. Body weight between 45 kg and 145 kg, inclusive, at screening9. Ability to comply with the study protocol, in the investigator's judgment

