4.2 Rationale for participant numbers and endpoint

The total sample size of 120 participants randomized in a 1:1 ratio to the two treatment groups is based on limitations in the available drug supply at this point in time. The current drug supply for MAS825 allow a maximum of 60 participants to be treated.

The primary endpoint for this study is the APACHE II score (range 0 to 71) on day 15 or on day of discharge (whichever is earlier) with worst case imputation for death as this disease severity score provides a comprehensive structured assessment of the clinical, physiological and laboratory parameters that have been routinely employed by physicians in the current situation to access the overall clinical status of COVID-19 patients with pneumonia and respiratory failure (Yang et al 2020, Wang et al 2020). In particular, the APACHE II disease severity score captures the clinically relevant physiologic variables for an aggregate score, with higher scores indicating more severe disease, with a median score of 18 reported for non-survivors of COVID-19. The APACHE II score will not be used by investigators to direct medical management of patients in this study.

To establish clinical efficacy based on APACHE II score, a sample size of 60 patients per treatment group provides 80% power when testing on an 10% 1-sided alpha level under the assumption that MAS825 in addition to SoC reduces the APACHE II score by 3.6 points more than placebo in addition to SoC (assumed standard deviation of 9.2 based on Yang et al 2020).

Commercially Confidential Information

Other clinical endpoints such as those derived from the 9-point ordinal scale were considered as primary endpoints. However, since these endpoints were binary in nature, the sample sizes required to have sufficient power to show statistically significant differences were much higher than those feasible with the limited available drug supply.

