6.3.2 Treatment assignment, randomization

At randomization visit, all eligible participants will be randomized via Interactive Response Technology (IRT) to one of the treatment arms. The investigator or his/her delegate will contact the IRT after confirming that the participant fulfills all the inclusion/exclusion criteria. The IRT

will assign a randomization number to the participant, which will be used to link the participant to a treatment arm.

The randomization numbers will be generated using the following procedure to ensure that treatment assignment is unbiased and concealed from participants and investigator staff. A participant randomization list will be produced by the IRT provider using a validated system that automates the random assignment of participant numbers to randomization numbers. These randomization numbers are linked to the different treatment arms. A randomization list will be produced by or under the responsibility of Novartis Global Clinical Supply (GCS) using a validated system that automates the random assignment of treatment arms to randomization numbers in the specified ratio.

Randomization will be stratified by:

- age (≤ 65 years, > 65 years)
- administration of any anti-viral therapy (e.g., hydroxychloroquine, chloroquine, convalescent plasma, remdesivir, faripivavir, ritonavir, lopinavir) as SoC (yes / no)
- presence of ≥ 1 of the following comorbidities: diabetes, hypertension, cardiovascular disease, chronic lung disease (yes / no)

The randomization scheme for participants will be reviewed and approved by a member of the Randomization Office.

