8.1.1 Information to be collected on screening failures

Participants who sign an informed consent form and subsequently found to be ineligible prior to randomization will be considered a screen failure. The reason for screen failure should be recorded on the appropriate CRF. The demographic information, informed consent, and Inclusion/Exclusion pages must also be completed for screen failure participants. No other data will be entered into the clinical database for participants who are screen failures, unless the participant experienced a serious adverse event during the screening phase (see [Section 10.1.3](#) for reporting details). If the participant fails to be randomized, the IRT must be notified within 2 days of the screen fail that the participant was not randomized.

Participants who are randomized and fail to start treatment, e.g. participants randomized in error, will be considered an early terminator. The reason for early termination should be recorded on the appropriate Case Report Form.

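### The primary analysis covers dosed participants only, so anyone randomised in either arm but never infused is left out, although the estimand compares randomised treatments

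*Protocol*

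**What the plan says.** On the analysis population, Protocol 12.4.2 states: "The analysis will be performed on the safety analysis set". SAP 6.1.3 repeats this. Protocol 12.1 and SAP section 4 define the set: "The Safety analysis set will include all randomized participants that have received any study drug". Within it, allocation is respected: "For all analysis sets, participants will be analyzed according to the study treatment(s) randomized".

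On the question being asked, Protocol 2.1 and SAP 6.1.1 take the randomised treatment as the treatment of interest. They say that the estimand should capture the effect on early discharge and on death within 14 days. A death on or before Day 15 receives the highest APACHE II score seen in any participant, and this overrides a discharge score. The one intercurrent event given a treatment-policy rule is discontinuation of treatment.

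On non-dosing, Protocol 8.1.1 has a category for it, with no restriction to one arm: "Participants who are randomized and fail to start treatment". It gives randomisation in error as an example and classes these people as early terminators. SAP 7.2.1 will tabulate them, with reasons.

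On other populations, the sensitivity analysis in SAP 6.1.4 uses PD analysis set 2, and the first supportive analysis in SAP 6.1.10 uses the PD analysis set. Both remove participants with certain protocol deviations. Neither, as worded, requires that the participant was dosed.

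**The concern.** The estimand is framed on what was assigned, but the analysis set also depends on an event after assignment, namely that an infusion was started. The people most likely to miss a planned infusion in this population include those who die or worsen quickly. Protocol 4.1 itself justifies rapid entry by the likelihood of early deterioration. These are the outcomes that the worst-score rule is there to count.

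Two things are at stake. The population analysed is narrower than the one the estimand describes. And if undosed participants fall unevenly between arms, by chance or otherwise, the comparison moves without any analysis of everyone randomised to show by how much. Dropping a bad outcome from the MAS825 arm favours MAS825; dropping one from placebo does the reverse.

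**Working it through.** **1. Set the rules side by side.**

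| Participant, either arm | Endpoint rule (Protocol 2.1, SAP 6.1.9) | In the primary ANCOVA? |
|---|---|---|
| Dosed, dies by Day 15 | Highest observed score | Yes |
| Infusion started, then stopped | Scored as if continued | Yes |
| Never dosed, dies by Day 15 | Highest observed score | No |
| Never dosed, alive | Day 15 or discharge score | No |

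The last two rows are the mismatch. Nothing technical prevents an undosed death from entering the model. Baseline is the last assessment before randomisation (SAP 4.1), the strata are known at randomisation, and the outcome is imputed.

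**2. Reproduce the plan's power.** Inputs from Protocol 12.9.1: 60 per arm, difference 3.6, SD 9.2, one-sided alpha 10%.

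- Standard error = 9.2 × √(2/60) = 1.68.
- 3.6/1.68 = 2.14, and 2.14 − 1.28 = 0.86, which gives power of 80.6% (80.4% with the noncentral t). The stated 80% reproduces.
- The smallest difference that would reach significance is about 1.2816 × 1.68 = 2.15 points.

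**3. Power lost by exclusion.** Same inputs, with k of 60 undosed:

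| k | One arm only | Each arm |
|---|---|---|
| 1 | 80.3% | 80.1% |
| 3 | 79.8% | 79.0% |
| 5 | 79.2% | 77.9% |

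Power is not the issue at plausible numbers.

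**4. Shift in an arm mean.** If k of 60 are dropped and their mean score is D points worse than that of the dosed, the arm mean moves by k × D/60.

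- One death scored 40 (assumed) against a mean of 14 (assumed): (40 − 14)/60 = 0.43 points. That is 0.43/3.6 = 12% of the planned effect, 0.43/1.68 = 0.26 standard errors, and 0.43/2.15 = 20% of the smallest significant difference.
- The imputed score is unknown in advance. If it were 30, the shift is 16/60 = 0.27 (7% of 3.6). If it were 55, the level that SAP 6.1.1 says is rarely exceeded, the shift is 41/60 = 0.68 (19%).
- Two undosed participants with D = 10 give 2 × 10/60 = 0.33. Five with D = 20 give 5 × 20/60 = 1.67; I have no basis for expecting that many.

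These are shifts in one arm's raw mean. Adjustment for baseline and strata would alter them somewhat, and similar exclusions in both arms would largely cancel.

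**The case against.** **Blinding makes a treated-only set reasonable.** Site staff are blinded, and the pharmacist who knows the allocation is independent of the study team (Protocol 6.4). An event before the infusion cannot be caused by the drug. If the decision to dose does not depend on arm, dropping undosed participants does not favour either arm in expectation. This stands, and it is why the expected effect is small. It does not make the analysed population match the estimand, and it does not remove chance imbalance.

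**The gap is short.** Imminent death within 24 hours is an exclusion criterion, and infusion may follow as soon as eligibility is confirmed. This also stands.

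**Never starting treatment is not an intercurrent event in the plan's terms.** The glossary places such events after treatment initiation. That is correct, so the treatment-policy rule is not itself contradicted. The death rule, however, is part of the endpoint and is not limited to dosed participants.

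**Other analyses may cover the undosed.** As worded, the PD sets could admit an eligible undosed participant, so the sensitivity analysis might include people whom the primary analysis omits. They still remove participants with deviations and so are not all-randomised analyses. A full analysis set appears in the abbreviation list, and the analysis-set and supportive-analysis sections contain redactions. A definition may lie there, and its absence is not held against the plan. It would not change the set that 12.4.2 names.

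**A stronger inference is tempting.** A reader may set "The current drug supply for MAS825 allow a maximum of 60 participants to be treated" beside "The total sample size of 120 participants randomized in a 1:1 ratio to the two treatment groups" and conclude that the exclusion can fall only on MAS825. The documents do not support that:

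- The set rule and Protocol 8.1.1 apply to both arms.
- The cap is described as current supply, Protocol 6.4 mentions re-supply, and enrolment is elsewhere given as "Approximately 120 male and female patients aged 18 years and above".
- Block size and any cap in the randomisation system are not given, and no section says that anyone would be assigned MAS825 with no drug available.

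If exactly 120 were allocated over 8 strata with blocks of 2 to 6, the chance of more than 60 MAS825 assignments would be about 30% to 37%, with a mean excess of only 0.4 to 0.6 participants. That is not a measure of bias. Running out of stock has no evident link to prognosis, while death before infusion, under blinding, has no evident link to arm.

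**Conclusion.** The mismatch is real: the primary analysis omits undosed participants in both arms, while the estimand is defined on randomised treatment and counts every death by Day 15. The public text shows no analysis of everyone randomised.

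The effect is probably small. One excluded death in an arm of 60 moves that arm's mean by about 0.43 points (0.27 to 0.68 for imputed scores of 30 to 55), against a planned 3.6, and the power loss for up to three undosed in one arm is under 1 percentage point. These shifts rest on assumed scores and an assumed count of undosed participants, since the documents give neither. No direction of bias can be claimed. The case for changing the plan is that the remedy is cheap and brings the analysis into line with the plan's own question.

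**What to change.** - In Protocol 12.4.2 and SAP 6.1.3, run the primary ANCOVA on all randomised participants, analysed as randomised. State explicitly that the existing exclusion for missing informed consent (SAP Table 4-1) carries over.
- In SAP 6.1.9, say that the death imputation applies to deaths by Day 15 whether or not the participant was dosed.
- Keep the safety set analysis as a sensitivity analysis.
- State whether the two PD sets require dosing, so that the populations can be compared.
- In Protocol 8.1.1, require vital status at Day 15 and APACHE II at Day 15 or discharge for undosed participants. Protocol 9.2 already provides contact at Days 29, 45 and 127 for those randomised and/or treated.
- Say how a living undosed participant with no Day 15 or discharge score will be handled. SAP 6.1.7 carries most components forward by no more than 4 days, and only if something was recorded at that visit.

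The cost is revised wording in both documents, follow-up of what should be very few patients, and possibly a few imputed or missing scores. The randomisation procedure does not need to change.
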